7.3 Pharmacokinetic assessments

Blood samples will be collected at specific time points according to [Table 2](#) for measurement of PK profile of nemolizumab and Antibodies anti-nemolizumab (ADA).

The nemolizumab serum exposure will be assessed at the following time-points: baseline, weeks 1, 2, 4, 8, 12, 16 and 18 and in case of early termination or any unscheduled visit for safety reason.

ADA will be assessed at baseline, weeks 4, 8, 12, 16 and 18 and or in case of early termination or unscheduled visit for safety reason.

7.3.1 Technical procedures for pharmacokinetic blood sampling

At each sampling time for PK assessment, 2 mL of blood will be collected for the assessment of nemolizumab concentrations in serum samples.

For ADA assessment, 2 mL of blood will be collected at the same time as PK sampling.

PK samples are to be collected before drug injection (pre-dose samples) at Baseline, weeks 4, 8; the maximum allowed time windows for PK blood sampling is 30 minutes before drug injection. At weeks 1, 2, 12, 16 and 18 blood samples will be collected at the corresponding usual time of drug injection with an allowed time window of ± 1 h.

The date and time of collection for each sample along with the time of the last study drug injection and missed injections have to be recorded on the eCRF.

Processing of blood samples for PK and ADA assessments will be described in a specific manual.

Volumes of blood to be obtained for PK, ADA tests are summarized in [Appendix 1](#).

7.3.2 Serum and PK analyses

Nemolizumab serum concentrations will be determined using validated ELISA method by a sponsor representative. A bioanalytical plan describing the details of the bioanalytical work related to serum samples of nemolizumab assessment will be written before the beginning of the sample analysis.

The results will be described in a bioanalytical report, which will be included as an appendix in the final clinical study report.

The PK analyses will be performed by a Sponsor representative. The results will be described in a PK report, which will be included in the final study report.

The PK parameters will be determined by a model independent approach (non-compartmental method) using individual serum concentration. Data from subjects with missing concentration values (missing samples) may be used if pharmacokinetic parameters can be estimated using the remaining data points.

When appropriate, the following PK parameters will be determined for each subject:

From baseline to week 4:

- C_{\max} : The observed peak drug concentration
- T_{\max} : The time at which C_{\max} occurs
- AUC_{0-t} : area under the concentration time curve calculated by the mixed linear logarithmic trapezoidal method from T_0 up to the sampling time corresponding to the last quantifiable concentration (C_{last})
- AUC_{0-28d} : Area under the concentration time curve from pre dose through 28 days post dosing. AUC_{0-28d} will be calculated by mixed linear logarithmic trapezoidal method

From week 12 to week 18 (or Early termination or Unscheduled visit if applicable):

- $t_{1/2}$: the terminal half-life value ($t_{1/2}$) will be calculated using the equation $\ln 2/k$ after the last drug injection (week 8).
- AUC_{0-t} : area under the concentration time curve calculated by the mixed linear logarithmic trapezoidal method from T0 up to the sampling time corresponding to the last quantifiable concentration (C_{last}).
- $AUC_{0-\infty}$: Area under the plasma concentration-time curve calculated by the mixed linear- logarithmic trapezoidal method from T0 and extrapolated to time infinity as: $AUC_{0-\infty} = AUC_{0-t} + C_{last} / k_{el}$. When the extrapolation represents more than 20%, $AUC_{0-\infty}$ and $t_{1/2}$ will not be reported.

At weeks 4, 8, 12, 16, 18 (or Early termination or Unscheduled visit if applicable):

- C_{trough} : The residual drug concentration

7.3.3 Anti-drug antibody analysis

ADA will be evaluated by a Sponsor representative using a validated ELISA screening assay. If serum circulating ADA is detected, they will be characterized using a validated assay. Incidence of positive ADA results will be summarized by treatment group (absolute occurrence and percent of subjects).

7.4 Pharmacodynamic assessments

Blood and skin samples (D-Squames and skin biopsies) will be collected to investigate the effect of nemolizumab on biomarkers.

As much as possible, skin sampling will be performed in similar body areas for all samples in all patients, on a selected area at baseline, such as the upper arms. Biopsies on prurigo lesions will be performed at baseline and post-treatment only for consenting subjects. Non-lesional sample will be taken at baseline in areas with no scratch such as the inner part of the upper arm approximately 5cm, apart from lesional skin.

The detail of the procedures for PD samples and storage conditions will be described in an Operational manual.

All collected samples will be sent to GALDERMA R&D for analysis. After performance of the planned investigations, the remaining samples will be integrated into the long term research program being performed in the research department of Galderma R&D (Program (2) – “Physiopathological study on skin disease to identify new dermatological medications; Initial declaration CP ECOH : DC-2008-315, 31/01/2009).

Volumes of blood to be obtained for PD tests are summarized in [Appendix 1](#).

7.4.1 Blood samples for PD

Blood samples for specific IgE will be collected at baseline only for all subjects. These samples will be analysed by the central laboratory.

Plasma samples will be collected at baseline, week 4 and week 12 for analysis of IL-31 protein expression levels for all randomized subjects.

7.4.2 D-Squames samples

Stratum Corneum (SC) samples will be collected for all randomized subjects using D-Squames to evaluate the microbiome, and cytokine and chemokine expression levels. SC samples will be collected for all randomized subjects at baseline visit, at Day 29 (week 4) and at Day 85 (week 12) as described below:

- Baseline visit (proteomic and microbiome analyses)
 - Non lesional skin
 - Lesional skin at baseline
- Week 4, day 29 (proteomic analysis only):
 - Lesional skin
- Week 12, day 85 (proteomic and microbiome analyses) :
 - Lesional skin

For proteomic analysis, 10 large rectangle D-squames (D100 Monaderm) will be used for consecutive tape stripping. Cytokine/chemokine profile including IL-31 will be performed using ELISA-like technologies. The 3 lesional samplings of D-squames at baseline, week 4 and week 12 will be taken on exactly the same anatomical location, no matter if the lesion regressed or not.

For microbiome analysis, one D-squame will be used (DS100 Monaderm, 2.2 mm diameter) being successively applied in the targeted area at least 20 times.

D-squames sampling should be performed as far as possible in a similar body location for every patient (e.g.upper arms) on selected areas and recorded in the CRF.

7.4.3 Skin biopsies

Three 4-mm skin biopsies will be performed (only for subjects who accept skin biopsies by signing the additional consent form) for IL-31 and IL-31RA quantification by immunohistochemistry techniques and IL-31 and IL-31RA mRNA by genomics analysis, if sufficient biological material is available.

Body location for biopsy sampling should be performed as far as possible in a similar body location for every patient (e.g. upper arms) and recorded in the eCRF.

The samples will be collected as much as possible on the same anatomical area than D-squames, in an adjacent lesion with as much as possible a similar clinical presentation.

Skin biopsies will be performed as it follows:

- Baseline visit:
 - One biopsy on lesional skin (nodule)
 - One biopsy on non lesional skin (e.g. inner arm): approx. 5 cm apart from lesion skin
- Week 12 (day 85) visit:
 - One biopsy on lesional skin after treatment (on a nodule selected at baseline)

7.5 Biophysical assessments

7.5.1 Actigraphy

High resolution actigraphy will be used in this study to evaluate scratching events and duration of sleep during the night. This is a non-invasive, ambulatory, wrist-mounted device designed to capture, record, and store all wrist movements, which is an indicator of whole body movement. The High resolution actigraphy provides an objective method for measuring scratching events during the night and other parameters such as sleep quality (Almazan et al 2016).

Philips will, in accordance with procedures, centrally analyze assessment data for scratching events and sleep parameters obtained from the actigraphy device and submit data to the CRO. Patients will wear two devices, one on each wrist, from D-7 and every day during the first 4 weeks of the study, by following the instructions provided by the CRO.

7.5.2 Whole body imaging

This device will be used in equipped sites only and the photographs of the entire body will be taken according to the operational manual provided by the Sponsor at least at baseline and Week 12 (Day 85) and if it is possible at Week 4 (Day 29), Week 8 (Day 57) , and Week 18 (Day 126). It is for illustration and as exploratory evaluation of the lesions improvement.

8 CLINICAL TRIAL VISITS DESCRIPTIONS AND PROCEDURES

8.1 Description of clinical trial visits

Please refer to the Schedule of Assessments table in the Synopsis ([Table 2](#)).

A written, signed ICF must be obtained prior to performing any clinical trial-related evaluations and/or procedures. The subject must be provided with a fully completed, dated and signed copy.

At each visit, assessments/procedures should be performed in the following order:

1. Patient-reported outcomes
2. Investigator assessments (including efficacy and safety)
3. Blood sample collection for laboratory assessments, PK and PD assessments
4. Administration of study drug

8.1.1 Screening period (Day -28 to Day -1)

8.1.1.1 *Visit 1 / Screening visit 1 (Day – 28 to Day -8)*

Screening visit 1 must be performed between Day -28 and -8 prior to Day 1 visit.

At this Screening visit, the Investigator or designee will:

1. Review and explain the nature of the study to the subject, particularly the prohibited activities and constraints.
2. Obtain the signed and dated ICF (and country-specific, photo and biopsy consent form if applicable) and provide a fully completed, dated and signed copy to the subject.
3. Collect information regarding demographics, relevant medical history, previous therapies and procedures, and concomitant therapies and procedures.
4. Assign the subject a SIN.
5. Perform a physical examination, vital signs measurements and ECG.
6. Conduct respiratory medical assessments, including PEF for subjects with a history of asthma.
7. Confirm that the subject meets inclusion/exclusion criteria for screening visit.
8. Complete serum pregnancy test if the subject is a female of childbearing potential.
9. Collect and record any AEs starting from the time of Informed Consent signature.

10. Collect blood sample for CPK, TB test, IgE analysis and viral serology
11. Ask the subject about the mean worst itch daily intensity over the previous 3 days according to NRS and record the information and record the information on the electronic device.
12. Schedule the Visit 2/Screening visit 2 and instruct the subject about the precautions to be taken for visit 2 (Avoid intensive sport, fasting condition for biochemistry analysis)

8.1.1.2 *Visit 2 / Screening visit 2 (Day -7)*

At this Screening visit, the Investigator or designee will:

1. Collect information regarding concomitant therapies and procedures and AEs.
2. Conduct respiratory medical assessments, including PEF for subjects with a history of asthma.
3. Check TB result previously performed. In case of inderminate results, collect blood sample to retest this parameter.
4. Check IgE & virology results
5. Collect blood sample for hematology, blood biochemistry.
6. Collect urine for urinalysis.
7. Instruct the subject on how to use the electronic device for the daily evaluation of pruritus NRS, VRS, sleep disturbance NRS. Remind the subject to report the assessments on a daily basis on the ePRO according to the protocol.
8. Provide the subject with electronic devices for pruritus assessments.
9. Instruct the subject on the use of the watches for Actigraphy
10. Provide the subject with the watches for Actigraphy assessments
11. Schedule the Visit 3/Day 1.

8.1.2 *Treatment period*

8.1.2.1 *Visit 3 / Baseline visit (Day 1)*

At the Baseline visit, the Investigator or designee will:

1. Ask the subject about AEs using an open-ended question, such as "Have you noticed any change in your health since the last visit?" Record all events, as appropriate, on the corresponding eCRF form(s).
2. Check laboratory results (hematology, biochemistry, virology, urinalysis, IgE, TB tests) from the Screening visits.

3. Complete urine pregnancy test if the subject is a female of childbearing potential.
4. Ask the subject about any changes in his/her concomitant therapies/procedures (added, removed or changed) since the previous visit. Record all changes in the source document and the eCRF.
5. Perform a physical examination (including height and weight), vital signs measurements and ECG.
6. Conduct respiratory medical assessments, including PEF for subjects with a history of asthma
7. Check subject's record for pruritus NRS and VRS and sleep disturbance NRS.
8. Confirm the eligibility of the subject according to inclusion and exclusion criteria. Enroll the subject in the clinical trial and record the corresponding SIN in the eCRF
9. Complete the evaluation of PAS and IGA.
10. Take whole body photographs (selected centers only).
11. Ask subject to complete the DLQI.
12. Check subject's use of watches for Actigraphy
13. Collect urine for urinalysis.
14. Collect blood sample for hematology, and entire blood biochemistry
15. Perform D-Squames.
16. Perform 4-mm biopsies for subjects who consented by signing the additional ICF
17. Collect blood samples for PK, ADA & biomarkers before drug injection.
18. The pharmacist (or other qualified personnel) will:
 - a. Prepare the syringe of dosing solution of appropriate volume of nemolizumab or placebo according to the pharmacy manual and the specific instruction provided by the IRT system;
 - b. Provide the prefilled syringe to the blinded investigator or qualified personnel for injection.
19. Blinded investigator or qualified personnel will administer the study drug subcutaneously to the subject, who will remain under medical observation for at least 30 minutes before been discharged.
20. Instruct the subject on how to use the electronic device to evaluate DPS 24, 48, and 72 hours after study drug administration, and remind subject about the daily evaluation of pruritus NRS, VRS and sleep disturbance NRS.
21. Complete the Subject Enrollment Log.
22. Schedule the next visit V4 Day 8.

8.1.2.2 *Visit 4 / Day 8 Week 1 (+/-1 day) & Visit 5 / Day 15 Week 2 (+/-2 days)*

The Investigator or designee will:

1. Collect information regarding AE (including review of laboratory values) and concomitant therapies/procedures.
2. Perform vital signs measurements.
3. Conduct respiratory medical assessments, including PEF for subjects with a history of asthma
4. When applicable check biopsy healing (for subjects who have consented).
5. Collect PK blood samples.
6. Check subject's record for pruritus NRS and VRS and sleep disturbance NRS
Remind the subject to evaluate NRS and VRS and sleep disturbance NRS daily by completing their device
7. Check subject's use of watches for Actigraphy
8. Schedule the next visit.

8.1.2.3 *Visit 6 / Day 29 Week 4 (+/-2 days) & Visit 7 / Day 57 Week 8 (+/-2 days)*

The Investigator or designee will:

1. Collect information regarding AE (including review of laboratory values) and concomitant therapies/procedures.
2. Perform physical examination & vital signs measurements (**including weight**).
3. Conduct respiratory medical assessments, including PEF for subjects with a history of asthma.
4. Perform ECG at visit 7/Day 57 only
5. Complete urine pregnancy test for female of childbearing potential only.
6. Complete the evaluation of PAS and IGA.
7. Check subject's record for pruritus NRS and VRS & sleep disturbance NRS
8. Ask subject to complete the DPS & DLQI before injection at Visit 6/Day 29 only
9. Collect the watches for Actigraphy analysis at Visit 6/Day29 only
10. Collect urine for urinalysis at Visit 6/Day29 only.
11. Collect blood sample for hematology and entire blood biochemistry, at Visit 6/Day29 only
12. Collect blood samples for biomarkers at Visit 6/Day29 only.

13. Collect PK blood samples for PK and ADA before drug injection.
14. Perform D-Squames sampling at Visit 6/Day29 only.
15. Take whole body photographs (selected centers only) if possible
16. Perform subcutaneous study drug injection and observe for at least 30 minutes before discharging the subject.
9. Remind the subject to complete the device daily
10. Schedule the next visit

8.1.2.4 Visit 8 / Day 85, Week 12 (+/- 5 days)

The Investigator or designee will:

1. Collect information regarding AE (including review of laboratory values) and concomitant therapies/procedures.
2. Perform physical examination (including weight) & vital signs measurements.
3. Collect blood samples for hematology & entire biochemistry.
4. Collect urine to perform urinalysis test.
5. Complete urine pregnancy test for female of childbearing potential only.
6. Conduct respiratory medical assessments, including PEF for subjects with a history of asthma.
7. Check subject's record for pruritus NRS and VRS and remind subject to complete them daily
8. Ask subject to complete the DLQI.
9. Complete the evaluation of PAS and IGA.
10. Collect blood samples for PK, ADA & biomarkers.
11. Perform D Squames.
12. Perform 4-mm biopsies for subjects who consented.
13. Take whole body photographs when applicable.
14. Schedule the next visit for Visit 9.

8.1.3 Follow up period

8.1.3.1 Visit 9 / Day 113, Week 16 (+/- 5 days)

The Investigator or designee will:

1. Collect information regarding AE (including review of laboratory values) and concomitant therapies/procedures.
2. Perform vital signs measurements.
3. Complete urine pregnancy test for female of childbearing potential only.
4. Conduct respiratory medical assessments, including PEF for subjects with a history of asthma.
5. Collect blood samples for PK, ADA
6. Control the good healing of biopsies when applicable.
7. Check subject's record for pruritus NRS and VRS and remind subject to complete them daily
8. Schedule the next visit for Visit 10.

8.1.3.2 *Visit 10 / Day 126, Week 18 (+/- 7 days)*

The Investigator or designee will:

1. Collect information regarding AE (including review of laboratory values) and concomitant therapies/procedures.
2. Check subject's record for pruritus NRS and VRS.
3. Perform physical examination & vital signs measurements.
4. Complete urine pregnancy test for female of childbearing potential only.
5. Conduct respiratory medical assessments, including PEF for subjects with a history of asthma.
6. Complete the evaluation of PAS and IGA.
7. Collect blood samples for PK, ADA
8. Take whole body photographs (selected centers only).
9. Collect the device used for Pruritus assessments
10. Complete the exit form.

8.1.4 *Early Termination visit or unscheduled visit:*

The Investigator or designee will:

1. Collect information regarding AE (including review of laboratory values) and concomitant therapies/procedures.
2. Check subject's record for pruritus NRS and VRS.
3. Ask subject to complete the DLQI.

4. Complete the evaluation of PAS and IGA.
5. Perform physical examination & vital signs measurements and ECG.
6. Conduct respiratory medical assessments, including PEF for subjects with a history of asthma.
7. Complete urinalysis.
8. Complete urine pregnancy test for female of childbearing potential only.
9. Collect blood samples for hematology & biochemistry
10. Collect blood samples for PK and ADA.
11. Complete the exit form in case of early termination and collect e-devices.

8.2 Subject instructions (other than study drug administration)

Throughout the study duration, subjects should be instructed to use their own moisturizer emollient including OTC preparations or bath oil. They will be instructed to avoid any topical product for pruritus relief containing capsaicin, menthol or other during the course of the study

Subjects will be instructed to avoid intensive physical exercise before blood sampling for biochemistry (CPK) to limit false positive and to come on site for Screening visit 2 in fasting conditions.

9 STATISTICAL METHODS PLANNED

9.1 Variables to be analyzed

9.1.1 Efficacy endpoints

The primary efficacy endpoint will be the percent change from baseline in NRS to week 4 (weekly average of the peak).

The secondary efficacy endpoints will be:

- Absolute and Percent change from baseline in weekly average of the peak and average pruritus NRS to each visit
- Change from baseline of VRS at each time point
- DPS
- PAS: Distribution for item 6 (excoriation/crusts and healed lesions stages) and change from baseline for item 5 (in lesions number)
- IGA: Distribution score and success rate (defined as IGA=0[clear] or IGA=1[Almost clear] with two point improvement from baseline).

9.1.2 Safety endpoints

The safety endpoint measures for this study are as follows:

- Adverse events
- Laboratory tests
- Vital signs
- Physical exam and body weight
- 12-lead ECG
- PEF

9.1.3 PK endpoints

The PK endpoints measures for this study are as follows:

- Serum IL-31 concentration
- Anti-CD14152 antibodies

9.1.4 PD endpoints

The pharmacodynamic endpoints measures for this study are as follows:

- Serum: IL-31 concentration
- Dsquames : IL-31, IL-31RA expression level and Cytokine/chemokine profiling in Dsquames
- Skin biopsies : IL-31 and IL-31 RA quantification by immunohistochemistry techniques and IL-31 and IL-31RA mRNA quantification by genomics analyses.

9.1.5 Other endpoints

- Quality of life (DLQI)
- Objective assessment of scratching and sleep with Actigraphy
- The sleep disturbance NRS

9.2 Statistical and analytical plans

A Statistical Analysis Plan (SAP) will be developed as a separate document. The SAP will contain detailed and technical description of specific data conventions, calculations and of statistical procedures for executing the analyses that are specified in the sections of the clinical trial protocol below.

Any changes made to analysis after finalization of SAP will be documented in the clinical study report.

9.2.1 Data transformations

9.2.2 Populations analyzed, evaliability and limitation / evaluation of bias

The statistical analyses will be performed based on the following subject populations.

9.2.2.1 *Intent-to-treat (ITT) Efficacy Population*

The ITT Population is defined as comprising all subjects who are randomized. All primary efficacy variables and secondary efficacy variables will be analyzed based on the ITT Population.

9.2.2.2 *Per-protocol (PP) Efficacy Population*

The PP Population is defined as comprising the ITT subjects who have no major protocol deviations. This will be the primary population for this study.

Major deviations are categorized into 4 categories:

- 1) Entrance criteria deviations,
- 2) Non compliance,
- 3) Concomitant therapies taken during the study, interfering with efficacy,
- 4) Administrative errors such as unblinding or study drug dispensing errors.

PP analysis will be conducted only up to Week 4.

9.2.2.3 *Safety Population*

The Safety Population is defined as comprising the ITT Population subjects who receive the study drug at least once. Randomized subjects will only be excluded if there is a clear documented evidence that the subject did not receive any study drug injection. All safety data will be summarized based on the Safety Population.

9.2.2.4 *PK analysis population*

The PK analysis population will include all subjects in the safety population who provide at least one post-baseline evaluable drug concentration value.

9.2.2.5 *PD analysis population*

The PD statistical analyses will be performed based on the PP population, and after exclusion of samples unable to produce reliable quantifications of cytokines, and/or immunohistological markers and/ or transcriptomic biomarkers, due to the material quantity and/or quality.

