9.2.4 Inferential statistical analyses

The primary efficacy analysis of the percent change from baseline to week 4 of the weekly average of the peaks pruritus NRS, will be an ANOVA including the Treatment group as factor, presence and absence of background of atopy and country as a cofactors.

In addition to the per-protocol analysis, several sensitivity analyses on ITT population will be conducted for the primary endpoint. For ITT, NRS will be set to missing after rescue medication is used.

- The primary imputation method for any missing data will be the LOCF (Last observation carried forward) approach.
- Multiple Imputation (MI) using the Missing At Random (MAR) assumption will also be used. The MI procedure of the SAS system will be used to generate five sets of data with missing values imputed from observed data. It is expected that the pattern of missing data will be monotonic, with slight deviations being corrected by the Markov Chain Monte Carlo (MCMC) method of the MI procedure. Linear regression will be employed to model the missing NRS score, with the following covariates included in the imputation model: treatment and non-missing data from earlier timepoints. The imputed datasets will be analyzed using the methodology described for percent change from baseline in NRS score. The results from the analysis of the multiple imputed datasets will be combined by the MIANALYZE procedure of the SAS system. The seed number to be used will be the protocol number (115828).

For secondary endpoints:

The percent change from baseline to any visits of the weekly average of the peak and of the average pruritus NRS, will be analyzed separately via an ANOVA including the Treatment group as factor, presence and absence of background of atopy and country as a cofactors. The absolute change will be analyzed via an ANCOVA, same factors as the percent change but with including baseline NRS as a covariate.

IGA, DPS and PAS will be analyzed at any visits by the CMH test stratified by background of atopy and by country with the ridit transformation and the row mean difference statistic (FREQ procedure from SAS).

Proportion of subjects achieving success (IGA=0[clear] or IGA=1[Almost clear] with two point improvement from baseline) will be analyzed at each evaluation visit using the Cochran-Mantel-Haenszel (CMH) test stratified by background of atopy and by country with the ridit transformation and the general association statistic (FREQ procedure from SAS).

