**PD Analysis Population (PDAP):**

The PD statistical analyses will be performed based on the PP population, and after exclusion of samples unable to produce reliable quantifications of cytokines, and/or immunohistological markers and/ or transcriptomic biomarkers, due to the material quantity and/or quality.

The efficacy summaries and analyses will be based on the ITT population, which is based upon the Intention-to-Treat (ITT) principle. In the event that a subject is allocated the incorrect study treatment as per the study randomization list, subjects will be summarized and analyzed 'as randomized' (i.e., by randomized treatment group). In the event that a subject is stratified incorrectly, 'randomized stratum' will be used rather than 'actual stratum'.

For the primary and selected secondary efficacy endpoints, a sensitivity analysis will be performed on the PP population to assess the robustness of the study conclusions to the choice of analysis population. Subjects will be included in the analysis according to the treatment 'as randomized'.

The safety summaries and analyses will be based on the SAF population. Randomized subjects will only be excluded if there is clear, documented evidence that the subject did not receive any study drug injection. In the event that a subject is allocated the incorrect study treatment as per the study randomization list, subjects will be summarized and analyzed 'as treated' (i.e., by allocated treatment group).

Upon database release, protocol deviation and analysis population outputs will be produced and will be reviewed by Sponsor. An analysis population classification meeting will be arranged to discuss the outputs and to decide which subjects and/or subject data will be excluded from certain analyses. Decisions made regarding the exclusion of subjects and/or subject data from analyses will be made prior to database lock and unblinding and will be documented and approved by Sponsor.

The following analysis population summaries will be provided:

- The number and percentage of subjects in each study population will be presented by study treatment group including total (Analysis population: ITT).

A by-subject listing of analysis population details will be provided. This listing will be presented by treatment group and will include: subject identifier, inclusion/exclusion flag for each population and reason for exclusion from each population. All randomized subjects will appear on this listing.

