The following derived and computed variables will be produced:

Variable Description	Computation Methods, Notes, or Equation(s)
Flag of ITT subjects	'Y' if subjects randomized into the study; otherwise 'N'
Flag of SAF subjects	'Y' if subjects in ITT and date and/or time of the first dose injection on Study Drug Administration form is non-missing; otherwise 'N'
Flag of PP subjects	'Y' if subjects in ITT who complete 12-week Treatment Period with the exception of major protocol violators who have significant effect on the efficacy; otherwise 'N'
Flag of PKAP subjects	'Y' if subjects in the safety population who provided at least one post-baseline evaluable drug concentration value; otherwise 'N'
Flag of PDAP subjects	'Y' if subjects in the PP, and after exclusion of samples unable to produce reliable quantifications of cytokines, and/or immunohistological markers and/ or transcriptomic biomarkers, due to the material quantity and/or quality; otherwise 'N'

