### 5.7 Efficacy Evaluation

Primary inference for efficacy analysis will be the percent change from baseline in NRS to week 4 (weekly average of the peak). This analysis will be based on the ITT population, and repeated using the PP population. Primary imputation method for any missing data including those who took rescue medication as failure will be the LOCF (last observation carried forward) approach. In addition, Multiple Imputation (MI) using the missing at random assumption will be conducted on ITT population:

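### Protocol V00 makes the per-protocol set primary and the SAP makes ITT primary; the switch is not recorded, and the sample-size rationale and per-protocol definition were not brought into line.

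*Protocol*

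**What the plan says.** **Protocol V00 (30 May 2017).** Section 9.2.2.1 says of ITT, defined as all randomised subjects: "All primary efficacy variables and secondary efficacy variables will be analyzed based on the ITT Population". Section 9.2.2.2 then says of PP: "This will be the primary population for this study". Section 9.2.4, repeated in the synopsis, reads: "In addition to the per-protocol analysis, several sensitivity analyses on ITT population will be conducted for the primary endpoint". Major deviations that remove a subject from PP include non-compliance and interfering concomitant therapies. Section 9.2.2.2 also limits the use of the set: "PP analysis will be conducted only up to Week 4".

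**SAP version 2.0.** Section 5.7 says of the primary inference: "This analysis will be based on the ITT population, and repeated using the PP population". Section 5.4 bases the efficacy analyses on ITT and adds that, for the primary and selected secondary endpoints, "a sensitivity analysis will be performed on the PP population to assess the robustness of the study conclusions". Section 1 lists one change, on pharmacokinetic calculations. In 5.11 the only specific change described is how ridit scores are computed. Section 5.10 keeps the protocol's sample-size argument, in which 30 per group is raised to 35 to hold power in the PP population.

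**PP definition in the SAP.** The text in 5.4 excludes subjects with major deviations that affect efficacy and has no completion requirement. The derivation table in the same section sets the flag to "Y' if subjects in ITT who complete 12-week Treatment Period", less the major violators.

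**The concern.** SAP 5.7.1 describes a superiority test. In such a test the randomised comparison is the protection against confounding, and ITT preserves it. PP drops subjects for what happens after randomisation. Poor compliance and resort to an interfering therapy can both follow from poor response, and at different rates in the two arms, so the remaining groups need not be comparable.

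The supplied protocol puts the primary test on that set and the SAP does not. A reader holding both finds two answers to which subjects carry the primary result, and no statement of when or why the answer changed. The sample-size paragraph in the SAP still belongs to the PP answer.

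**Working it through.** **1. The passages side by side**

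| Place | ITT | PP |
|---|---|---|
| Protocol 9.2.2.1 | primary and secondary variables analysed | – |
| Protocol 9.2.2.2 | – | primary population |
| Protocol 9.2.4, synopsis | sensitivity, for the primary endpoint | the analysis the ITT ones are added to |
| Protocol 9.3.3 | – | set whose power is protected |
| SAP 5.4, 5.7 | primary | sensitivity |
| SAP 5.10 | – | set whose power is protected |
| SAP 1, 5.11 | no switch recorded | no switch recorded |

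Within the protocol, 9.2.2.1 can be reconciled with 9.2.2.2 by reading it as saying that ITT is also analysed. Between protocol and SAP the roles are plainly exchanged.

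**2. The plan's sample size reproduces**

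Inputs (protocol 9.3.2 and 9.3.3, SAP 5.10): difference 30, SD 35, two-sided 5%, power 90%, 1:1 allocation. Effect size d = 30/35 = 0.857.

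- Normal approximation: n = 2 × (1.960 + 1.282)² / 0.857² = 28.6, so 29 per group.
- Two-sample t-test: n = 29.6, so 30 per group, as stated.
- Loss allowed for: 1 − 30/35 = 14.3%. The documents give no dropout rate; this is what 30 of 35 implies.

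**3. Power on each set**

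The t-test has noncentrality d × √(n/2) and 2n − 2 degrees of freedom.

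- PP with 30 per group left: 0.857 × √15 = 3.32, power 90.4%.
- PP with 10% excluded (31.5 per group): 91.7%. With 20% excluded (28 per group): 88.3%.
- ITT with 35 per group and the full effect in everyone: 0.857 × √17.5 = 3.59, power 94.2%.

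The last figure is optimistic, because ITT keeps the subjects PP would drop. Suppose a share f of randomised subjects contributes no treatment difference. The mean difference becomes 30 × (1 − f). The shares are assumptions, and the SD is held at 35.

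| f | Difference | ITT power, 35 per group |
|---|---|---|
| 0% | 30.0 | 94.2% |
| 5% | 28.5 | 91.9% |
| 10% | 27.0 | 88.9% |
| 14.3% | 25.7 | 85.8% |
| 15% | 25.5 | 85.2% |
| 20% | 24.0 | 80.7% |

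Power falls below 90% at a share of roughly 8%.

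**4. What exclusions could do to the estimate**

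The documents give no response for excluded subjects, so only a hypothetical case is possible. Assume arm means of −50% (nemolizumab) and −20% (placebo), with 5 of 35 excluded.

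- Excluded nemolizumab subjects at −20%: (35 × (−50) − 5 × (−20))/30 = −55.0. The effect against −20 rises from 30 to 35.0.
- Excluded placebo subjects at 0%: (35 × (−20) − 5 × 0)/30 = −23.3. The effect against −50 falls from 30 to 26.7.
- Both together: 55.0 − 23.3 = 31.7, a net shift of 1.7.

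The sign depends on which arm loses whom. The example shows that PP can move the estimate either way, and says nothing about what would happen in this trial.

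**5. The two PP sets differ**

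The protocol stops PP analysis at Week 4. The SAP flag requires completion of the 12-week period, which SAP 5.3.1 defines as completing the Week 12 visit. Under the flag, a subject who provides the Week 4 endpoint and later leaves, for example for lack of efficacy (a listed reason in protocol 5.8), is removed from the Week 4 PP analysis because of an event after the endpoint. Under the SAP's own text definition, leaving would not by itself exclude that subject.

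**The case against.** The strongest reply is that the two documents are not of the same generation. The supplied protocol is V00. SAP section 2 says the SAP is written to All Countries Amendment 2.0 of 9 April 2018. Other differences suggest the plan moved on in between: V00 allows an interim analysis (9.4) and the SAP plans none (5.7.1.5). If the amendment made ITT primary, the SAP reverses nothing and 5.11 has nothing to list. This stands as a limit, because the amendment is not available to check. It would not account for the PP-based sample-size text in SAP 5.10 or the two PP definitions inside SAP 5.4.

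A reader might infer that the sponsor is free to present whichever result looks better. The documents do not support that. The SAP is consistent on ITT, and 5.4 requires exclusions to be decided and documented before database lock and unblinding. If the SAP governs, the headline analysis is identifiable; what is missing is a recorded reason for the change.

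A reader might also infer that PP would inflate the effect. That is not shown. One response-dependent route is limited: rescue for pruritus is permitted only from Day 29 (protocol 5.7), after the Day 22 to 28 diary window for Week 4 (SAP 5.2). Non-compliance and prohibited therapies remain as routes.

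Nor is the move to ITT free. The 94% figure would suggest that nothing is lost, but it assumes a full effect in every randomised subject.

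**Conclusion.** The point holds as a conflict over the primary population between protocol V00 and the SAP, with no record of the change in the SAP. It should be corrected. It does not invalidate the SAP's primary analysis, since the SAP already makes the sounder choice.

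No bias figure can be attached to it. The effect on power can be bounded under stated assumptions. With ITT primary at 35 per group, power is 94% at best, about 89% if a tenth of subjects contribute no treatment difference, and about 86% if the 14% that the plan allows for do so. These rest on the plan's difference of 30 and SD of 35 and on assumed shares. The sample-size arithmetic itself is sound; its rationale refers to a set that is no longer primary.

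**What to change.** - Name ITT as the sole primary population in protocol 9.2.2.1, 9.2.2.2, 9.2.4 and the synopsis, with PP as a sensitivity analysis.
- Record the change and its reason in SAP 5.11. If Amendment 2.0 already made it, cite that amendment there instead.
- Give one PP definition in both documents and in the SAP derivation table. For a Week 4 endpoint it should not depend on completing 12 weeks. The pharmacodynamic population is built on PP, so state whether it follows the same definition.
- Restate the sample-size rationale in protocol 9.3.3 and SAP 5.10 for ITT, saying what share of subjects without a treatment difference 35 per group can absorb (roughly 8% before power drops below 90%).

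The cost is wording in two documents, with no new data or procedures. The real cost is accepting that ITT power may fall below the planned 90% if more than that share contributes no difference.
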